7. DATA COLLECTION

Data collection for primary, secondary and safety clinical outcomes

Data will be collected by the research team from routinely available NHS hospital records or trial specific documentation and will include the following categories: eligibility criteria, consent and baseline demographics, comorbidities, regular treatment, ECG results, vital signs, blood results, admission and discharge diagnoses, cardiology and other relevant investigations or interventions, length of stay, repeat hospitalisations and adverse events. Detail will also be collected on the trial intervention including timing, details of the procedure including dose, reporting clinician, report including incidental findings, and any adverse events as a result of the intervention.

Collection of cost and health outcome data

Length of stay and major adverse cardiac events will be recorded from telephone contact of patients, hospital and primary care records, and deaths from the Central Registry Office or equivalent. At baseline, 1, 6 and 12 months, quality of life and angina symptoms will be measured using the EQ-5D-5L and ROSE questionnaires by direct patient interview, postal or email survey with telephone follow up for non-responders after two mailings two weeks apart.

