In general, analyses will be adjusted for study site (used to stratify the randomisation), baseline GRACE score (continuous), and previous CAD (yes/no), unless otherwise specified. Of note, study site will be included as a random effect (as there will be a large number of sites); whilst GRACE score, and previous CAD will be included as fixed effects. GRACE score will be adjusted for using a restricted cubic spline with 3 knots (thus using 2 degrees of freedom). The knots will be placed at the following percentiles of the predictor's marginal distribution: 0.1, 0.5, 0.9. Age is contained within GRACE score and will therefore not be adjusted for separately. Baseline GRACE score will be calculated from individual components, using the formula for predicting death or non-fatal MI within 6 months of admission with ACS [2], rather than using the GRACE score field in the database.

All analyses and data manipulations will be carried out using the most up to date version of SAS available [1].

4. List of Analyses

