Routine admission blood tests: Urea (mmol/L) [continuous], Creatinine (μmol/L) [continuous], Estimated glomerular filtration rate (ml/minute/1.73m²) [categorised], Alanine aminotransferase (Units/L) [continuous], Haemoglobin (g/L) [continuous], White blood cell count (x10⁹/L) [continuous], Random blood glucose (mmol/L) [continuous], Cholesterol (mmol/L) [continuous].

Observations within 60 minutes prior to randomisation: Respiratory rate (breaths per minute) [continuous], Oxygen saturation (SpO₂ %) [categorical], Fraction inspired oxygen (%) [categorical], Heart rate (beats per minute) [continuous], Systolic blood pressure (mmHg) [continuous], Diastolic

Statistical Analysis Plan	RAPID-CTCA
Version No	2.0
Date Finalised	19 Aug 2020

blood pressure (mmHg) [continuous], Capillary blood glucose (mmol/L) [continuous], Temperature (°C) [continuous].

Treating clinical impression at time of randomisation: ACS [categorical], Diagnosis [categorical], Diagnosis certainty ((0-10 where 0 is the least certain and 10 is the most certain) [continuous]

Concomitant medication: Beta blocker, Calcium channel blocker, ACE Inhibitor or ARB, Nicorandil, Oral nitrate, Buccal or sublingual nitrate, Oral hypoglycaemic, Insulin, Statin, Aspirin, Clopidogrel, Prasugrel, Ticagrelor, TNK/TPA, LMWH, Tirofiban or equivalent 2B3A inhibitors, Intravenous nitrate (including infusion), Fondaparinux, Unfractionated heparin, Bivalirudin, Novel anticoagulants, Intravenous morphine/opiate, Diuretic, Proton Pump Inhibitor, Ivabradine, Warfarin, Ranolazine.

Table: N (%) with any of medications listed prescribed before admission [Y/N] and N (%) for each medication, by treatment arm, and overall.

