9. Proportion of patients discharged on preventative treatment or have alteration in dosage of preventative treatment during index hospitalisation;

Statistical Analysis Plan	RAPID-CTCA
Version No	2.0
Date Finalised	19 Aug 2020

Table: N (%), odds ratio with 95% confidence interval; using logistic regression adjusted as specified earlier, with unadjusted analysis also presented.

Primary or secondary prevention treatment includes beta blocker, calcium channel blocker, ACE inhibitor or ARB, nicorandil, oral nitrate, buccal or sublingual nitrate, oral hypoglycaemic, insulin, statin, aspirin, clopidogrel, prasugrel, ticagrelor.

10. Length of stay for index hospitalisation;

This will be reported in Hours

Table: Descriptive statistics [continuous data].

Table: Difference between the intervention groups with 95% confidence interval, using Hodges Lehmann estimator of location shift, with a Moses distribution free confidence interval based on the Wilcoxon Rank Sum test.

11. Representation or rehospitalisation with suspected ACS/recurrent chest pain within 12 months [NB this is being interpreted as time from randomisation, not time from index hospitalisation]

This will be measured as the time from randomisation to the first relevant event. Patients discontinuing the study (for any reason) prior to reaching the outcome will have their time to outcome censored at the last contact date. Patients who die before achieving the outcome, will have their time to outcome censored at the date of death.

If the proportional hazards assumption holds, using visual inspection, then the relationship between intervention and this outcome will be analysed using Cox proportional hazard regression. The results will be expressed as a hazard ratio with the corresponding 95% confidence intervals and p-value. The primary analysis will be adjusted as specified in the Overall Statistical Principles section of this document. An unadjusted analysis will also be presented, as a sensitivity analysis.

The number of patients with an outcome event (by treatment group) will be tabulated, and the following statistics will be presented: adjusted HR (and 95% CI, p value), unadjusted HR (and 95% CI, p value). A Kaplan-Meier plot will be produced, showing results by allocated treatment.

12. Chest pain symptoms up to 12 months;

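### The model for preventative treatment at discharge (SAP 4.6, item 9) omits pre-admission use of the same drugs, which is collected and is in effect the outcome's baseline value; this costs precision in a descriptive estimate

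*SAP*

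**What the plan says.** Item 9 of SAP 4.6 is the "Proportion of patients discharged on preventative treatment or have alteration in dosage of preventative treatment during index hospitalisation". Its drug list begins "Primary or secondary prevention treatment includes beta blocker, calcium channel blocker, ACE inhibitor or ARB, nicorandil, oral nitrate" and runs to 13 classes, ending with statin, aspirin and three other antiplatelets. The analysis is a table of counts and an odds ratio with 95% CI, "using logistic regression adjusted as specified earlier, with unadjusted analysis also presented". Item 8, ACS therapies during the index stay, has the same model with eight drug classes.

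The adjustment referred to is in SAP section 3: "In general, analyses will be adjusted for study site (used to stratify the randomisation), baseline GRACE score (continuous), and previous CAD (yes/no"), with site as a random effect and GRACE score as a spline. That section allows an outcome to specify something else. Items 8 and 9 do not.

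Protocol section 7 lists "consent and baseline demographics, comorbidities, regular treatment, ECG results, vital signs" among the data collected. SAP 4.2 tabulates "N (%) with any of medications listed prescribed before admission [Y/N] and N (%) for each medication, by treatment arm, and overall". The baseline list contains all 13 classes of item 9 and all eight of item 8.

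SAP 4.6 opens by making every p-value in that section descriptive.

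**The concern.** Item 9 counts being on treatment at discharge, or having a dose altered. It does not count starting treatment. Someone already taking a statin or insulin who goes home on it is a success whichever arm they were in, so prior use predicts the outcome through the definition itself. It is measured before randomisation and costs nothing further to obtain, yet it is only tabulated.

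Previous CAD is a partial stand-in. The list includes insulin, oral hypoglycaemics, ACE inhibitors or ARBs and calcium channel blockers, which patients without CAD may also take.

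The comparison is of interest because treatment use is the third secondary objective (Protocol 2.1.2), and better preventive prescribing is one of the routes by which CTCA is expected to help (Protocol 1.1). At stake are the precision of that estimate and its exposure to a chance difference between arms in prior drug use.

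**Working it through.** **No stated figure for item 9.** The documents give no rate, effect or power for items 8 or 9. The 1,720 patients in Protocol 4.1 are sized for the primary outcome (the figure reproduces as 8.5% versus 5.1%, 860 per arm, 80% power). It is used here only as N, with 1:1 allocation.

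**Assumptions.** Previous CAD 35%. The other rates are in the table, and none comes from the documents. The comparator model contains previous CAD and stands in for the planned model without the GRACE spline and site. The second model adds prior use (yes/no). Equivalent-N gain = (z with prior use ÷ z without)², where z = ln(OR) ÷ SE.

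| Prior use, CAD / no CAD | Control outcome, users / non-users | OR without → with prior use | SE of log OR | Equivalent-N gain |
|---|---|---|---|---|
| 60% / 40% | 80% / 70% (weak) | 1.39 → 1.40 | 0.116 → 0.117 | ×1.01 |
| 90% / 50% | 90% / 60% (moderate) | 1.35 → 1.40 | 0.126 → 0.133 | ×1.11 |
| 90% / 50% | 95% / 50% (strong) | 1.30 → 1.40 | 0.125 → 0.143 | ×1.29 |
| 95% / 50% | 98% / 50% (strong) | 1.28 → 1.40 | 0.134 → 0.156 | ×1.36 |
| 95% / 30% | 98% / 40% (strong) | 1.35 → 1.50 | 0.118 → 0.137 | ×1.34 |
| 95% / 50% | 99% / 30% (extreme) | 1.24 → 1.50 | 0.122 → 0.169 | ×1.89 |

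Fourth row by hand: z = ln(1.28) ÷ 0.134 = 1.84 without prior use and ln(1.40) ÷ 0.156 = 2.16 with it. (2.16 ÷ 1.84)² is about 1.37, against 1.36 before rounding.

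**The same question on a scale where the target does not move.** The odds ratio changes when the covariate is added, so take the standardised risk difference. Its variance is V ÷ 1720 with V = 2A + 2B + D. A and B are the averages of p(1 − p) over covariate strata in the control and CTCA arms, and D is the between-stratum variance of the risk difference. For the fourth row:

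- Prior use overall: 0.35 × 0.95 + 0.65 × 0.50 = 0.6575. CTCA-arm rates at OR 1.4: users 0.9856, non-users 0.5833. Risk difference: 0.6575 × 0.0056 + 0.3425 × 0.0833 = 3.2 points.
- Unadjusted: rates 0.8156 and 0.8478, V = 2(0.1504 + 0.1290) = 0.559, SE 1.80 points.
- Previous CAD: rates 0.956 and 0.9655 with CAD, 0.740 and 0.7845 without. A = 0.35 × 0.956 × 0.044 + 0.65 × 0.740 × 0.260 = 0.1398; B = 0.1216; D = 0.0003. V = 0.523, SE 1.74 points.
- Prior use added: A = 0.6575 × 0.98 × 0.02 + 0.3425 × 0.50 × 0.50 = 0.0985; B = 0.0926; D = 0.0014. V = 0.3835, SE 1.49 points.
- Ratio: 0.523 ÷ 0.3835 = 1.36.

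The moderate row gives A = 0.1615, B = 0.1343, D = 0.0001 (V = 0.592) with previous CAD, and A = 0.1440, B = 0.1223, D = 0.0006 (V = 0.533) with prior use added. The ratio is 1.11 and the SE falls from 1.85 to 1.76 points. Simulated trials of 1,720 patients under other moderate to strong assumptions gave gains of about ×1.05 to ×1.47.

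**Chance imbalance.** With prior use at 66%, the between-arm difference in prior use has SD √(2 × 0.6575 × 0.3425 ÷ 860) = 2.3 points. In the fourth row a 1-SD imbalance moves the crude outcome difference by 2.3 × (0.98 − 0.50) = 1.1 points, against a true difference of 3.2. Previous CAD removes part of that and the unadjusted analysis removes none.

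**Item 8.** Four of its eight classes are acute hospital treatments (thrombolytic, LMWH, 2B3A inhibitor, intravenous nitrate). Prior use can carry over mainly through the four antiplatelets. With assumed in-hospital treatment of 75–90% in prior users and 60–75% in non-users, the gain is about 0–2%.

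**The case against.** A reader might infer that the trial loses power. It does not lose any that the plan relies on: SAP 4.6 makes these p-values descriptive, items 8 and 9 promise only counts and an odds ratio with its interval, and no formal conclusion rests on them. That objection stands.

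A reader might also expect the extra term to narrow the reported interval. On the log odds ratio scale it does the reverse (0.134 to 0.156 in the fourth row), because the odds ratio becomes conditional on one more covariate and moves away from 1. This stands for the odds ratio. It does not remove the gain, since the standardised risk difference has the same target in both models and its variance falls.

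It is tempting to treat items 8 and 9 alike. The documents do not support that prior use largely determines item 8, given its acute drugs and a population admitted with suspected or confirmed ACS.

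The size is assumed. The comparator also lacks the GRACE spline, which carries age, and the site effect, so the gain over the model actually planned was not estimated.

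Finally, one covariate set for all outcomes is an ordinary safeguard against choosing covariates outcome by outcome, and Protocol section 8 gives secondary outcomes the same adjustment as the primary. That is fair, but a term fixed in advance and justified by the outcome definition does not invite selection, and SAP section 3 leaves room for exceptions. The by-arm table of prior drug use would reveal an imbalance without correcting it.

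**Conclusion.** The point holds for item 9 and is minor. The covariate is omitted, is measured before randomisation, and is tied to the outcome by the outcome's own definition. Under assumed rates with prior use a moderate to strong predictor, including it is worth roughly 5% to 50% in equivalent sample size over a model with previous CAD. The gain is near zero if prediction is weak and reached ×1.89 only at an extreme assumption. These figures rest on 1,720 patients, conditional odds ratios of 1.4 to 1.5 and drug-use rates that the documents do not give.

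What is lost is precision and balance in a descriptive estimate. No confirmatory result depends on it. For item 8 a worthwhile gain is not shown.

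**What to change.** In SAP 4.6 item 9, state that the logistic model carries the general adjustment plus one yes/no term for pre-admission prescription of any drug in the item's own list. Keep the unadjusted result. Report a standardised risk difference with 95% CI beside the odds ratio, and name the odds ratio as conditional on prior use. State in advance that a penalised or stratified fit will be used if nearly all prior users have the outcome.

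For item 8, at most add pre-admission antiplatelet use (yes/no) as a sensitivity analysis.

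Cost: one SAP sentence, one model term and a standardisation step, with no new data. Because Protocol section 8 describes a common adjustment, record the change as a justified exception. If it is made after the arms have been compared, label it post hoc.

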SCOT-HEART	Trial acronym for 'Scottish Computed Tomography of the Heart' trial
SD	Standard Deviation
SOP	Standard operating procedure
SPO2	Peripheral capillary oxygen saturation
TNK/TPA	Tenecteplase/Tissue plasminogen activator
TSC	Trial Steering Committee
U	Units
Y/N	Yes/No

1. Introduction

This document details the criteria to be used for the definition of the analysis populations and the statistical methodology for analysis for the RAPID-CTCA trial, a randomised controlled trial of early computed tomography coronary angiography (CTCA) in patients presenting with suspected/confirmed acute coronary syndrome (ACS) to Emergency Departments (ED) and Medical Assessment Units.

This document has been compiled according to the Edinburgh Clinical Trials Unit (ECTU) standard operating procedure (SOP) "Statistical Analysis Plans" ECTU_ST_04 and has been written based on information contained in the study protocol version 7.0, dated 24 February 2020.

RAPID-CTCA is a multicentre, randomised, parallel-group open trial. Randomisation is at the individual level with a 1:1 allocation ratio, and is stratified by study site. Patients are randomised to either CTCA in addition to standard care or standard care alone. The aim was originally to recruit 2,500 patients in about 30 NHS tertiary and district hospitals (with or without on-site coronary angiography facilities) with emergency departments, acute medical, radiology, and cardiology services. This was updated to a size of at least 1735 in protocol version 7.

2. Statistical Methods section from the protocol

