Subgroup analysis on the primary outcome is planned for age ($<65/\geq 65$ years), sex (Male/Female), baseline GRACE score (grouped as <109 , 109-139, 140 or more), previous CAD (Y/N), baseline ECG result (normal/abnormal), baseline troponin concentration (initial measurement above/below the 99th centile for the site-preferred assay – sex specific where available), and presentation to a study site with or without on-site invasive coronary angiography facilities.

These will be assessed by examining the effect of entering the treatment by subgroup interaction into the Cox regression model. The ratio of hazard ratios, plus 95% confidence interval, will be given for the interaction. Within subgroup treatment effect estimates and confidence intervals will also be presented. If time allows, this will be presented as a forest plot.

We will also prepare a table or graph of effect size by centre for the primary outcome, for the 5 largest sites (all randomised >100 patients). This will not involve any formal statistical testing.

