4.6 Other secondary outcomes

Any p-values presented will be for descriptive purposes only, and should not be considered as formal statistical significance testing.

1. Coronary Heart Disease (CHD) death or subsequent non-fatal MI (type 1 or 4b);

This will be measured as the time from randomisation to the first relevant event. Patients discontinuing the study (for any reason) prior to reaching the outcome will have their time to outcome censored at the last contact date. Patients who die from a cause that is not part of the outcome, before achieving the outcome, will have their time to outcome censored at the date of death.

The analysis will use adjudicated outcome data, where these are available and relevant.

If the proportional hazards assumption holds, using visual inspection, then the relationship between intervention and this outcome will be analysed using Cox proportional hazard regression. The results will be expressed as a hazard ratio with the corresponding 95% confidence intervals and p-value. The primary analysis will be adjusted as specified in the Overall Statistical Principles section of this document. An unadjusted analysis will also be presented, as a sensitivity analysis.

The number of patients with an outcome event (by treatment group) will be tabulated, and the following statistics will be presented: adjusted HR (and 95% CI, p value), unadjusted HR (and 95% CI, p value). A Kaplan-Meier plot will be produced, showing results by allocated treatment.

2. Subsequent Non-fatal MI (type 1 or 4b);

This will be measured as the time from randomisation to the first relevant event. Patients discontinuing the study (for any reason) prior to reaching the outcome will have their time to outcome censored at the last contact date. Patients who die from a cause that is not part of the outcome, before achieving the outcome, will have their time to outcome censored at the date of death.

The analysis will use adjudicated outcome data, where these are available and relevant.

If the proportional hazards assumption holds, using visual inspection, then the relationship between intervention and this outcome will be analysed using Cox proportional hazard regression. The results

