4.8 Other analyses

Cost effectiveness analysis is specified in the Health Economics Analysis Plan

Clinical investigations during trial (these may be re-categorised after taking in to account the text from the 'other relevant' category):

- Echo (Yes/No)
- Radionuclide scan (Yes/No)
- 24 hour tape (Yes/No)
- Abdominal ultrasound (Yes/No)
- Upper gastrointestinal endoscopy (Yes/No)
- Exercise test (Yes/No)
- MRI angiography (Yes/No)
- Stress echo (Yes/No)
- Result of final ECG
- Rhythm of final ECG
- Abnormal final troponin (Yes/No)
- Other relevant, as specified on categorisation of 'other investigations' by Chief Investigator

Clinical process:

- Most applicable disposition place (place sent after initial attendance location)
- Most applicable discharge diagnosis

5. Validation and QC

The following will be done by a second statistician:

1. Separate programming and checking of primary outcome results and conclusions.
2. The statistical report will be read and sense-checked.

6. Data sharing

A file, or set of files, containing the final analysis data will be prepared as part of the final analysis. Within the University of Edinburgh environment, under certain safeguards, these de-identified datasets can be shared. If a fully anonymised version is required for external sharing, further discussion is needed.

7. References

1. SAS® Institute Inc. SAS for Windows. SAS Institute Inc.: Cary, NC, U.S.A
2. Fox et al for the GRACE Investigators. Prediction of risk of death and myocardial infarction in the six months after presentation with acute coronary syndrome: prospective multinational observational study (GRACE). *BMJ* 2006; 33:1091-1094.

RAPID-CTCA_SAP v2.0

Final Audit Report

2020-08-26

Created:	2020-08-19
By:	[name] ([contact])
Status:	Signed
Transaction ID:	CBJCHBCAABAAM8vR534O7SLn6kZJDglwhbxvkB7mTVti

"RAPID-CTCA_SAP v2.0" History

 Document created by [name] ([contact])

2020-08-19 - 14:43:43 GMT- IP address: [name]

 Document emailed to [name] ([contact]) for signature

2020-08-19 - 14:57:28 GMT

 Email viewed by [name] ([contact])

2020-08-19 - 14:57:58 GMT- IP address: [name]

 Document e-signed by [name] ([contact])

Signature Date: 2020-08-19 - 14:58:39 GMT - Time Source: server- IP address: [name]

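### Length of stay is the only SAP outcome with an effect estimate and 95% CI but no site-adjusted result; if stay varies between hospitals, its interval is valid but somewhat wider than it need be

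*SAP*

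**What the plan says.** SAP 1 (Introduction) states: "Randomisation is at the individual level with a 1:1 allocation ratio, and is stratified by study site". Protocol 5.4.1 agrees.

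SAP 3 sets the default: "analyses will be adjusted for study site (used to stratify the randomisation), baseline GRACE score (continuous), and previous CAD (yes/no), unless otherwise specified". Site is to enter as a random effect, because there are many sites.

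For length of stay in hours, SAP 4.6 item 10 gives descriptive statistics and a between-arm difference "using Hodges Lehmann estimator of location shift, with a Moses distribution free confidence interval based on the Wilcoxon Rank Sum test". It lists no adjusted or stratified companion. Item 9, immediately before it, is analysed "using logistic regression adjusted as specified earlier, with unadjusted analysis also presented".

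On all of 4.6 the SAP says: "Any p-values presented will be for descriptive purposes only, and should not be considered as formal statistical significance testing". Protocol 8 calls for suitable nonparametric methods for continuous outcomes that are not normally distributed.

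**The concern.** Stratified allocation makes the arms similar in their mix of hospitals, so differences between hospitals largely cancel out of the comparison. The pooled rank-sum interval is calculated as if that balance had not been imposed, so it still counts between-hospital variation as noise. If stay varies by hospital, the interval covers more than 95% of the time and is too wide.

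The documents give reasons to expect some variation. Sites include hospitals with and without on-site angiography (Protocol 3), and angiography often means transfer between hospitals (Protocol 1.1).

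Length of stay is a named secondary objective (Protocol 2.1.2), and shorter stay is one of the NHS benefits claimed (Protocol 1.1). Because its p-values are descriptive, the estimate and interval carry the between-arm comparison. Only the width of that interval is at stake, not bias or false-positive error.

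**Working it through.** **Inventory.** Outcomes in SAP 4.4–4.6 with an effect estimate and 95% CI:
- Primary outcome: 1, adjusted and unadjusted hazard ratio.
- Key secondary outcomes: 6, the same.
- Section 4.6 items 1–7 and 11: 8, the same.
- Section 4.6 items 8 and 9: 2, adjusted and unadjusted odds ratio.
- Section 4.6 item 10, length of stay: 1, unadjusted only.

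Total 1 + 6 + 8 + 2 + 1 = 18, of which 17 have a site-adjusted result. Items 12–14 are descriptive and item 15 is left to the Health Economic Analysis Plan, so none is a counter-example. The by-centre display in 4.4 concerns the primary outcome.

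**Inputs.** The documents give no figure for stay to reproduce. They do give at least 1,735 patients and about 35 sites (Protocol 4.1 and 3), 1:1 allocation within site, and five sites with more than 100 patients each (SAP 4.4). The rest is assumed:
- Site sizes: five of 250, 190, 160, 140 and 120, and thirty of 4–66.
- Permuted blocks of 4.
- Log-normal stay, median 24 h, log-SD 1.0 (also 0.7 and 1.3).
- ICC, the between-site share of log-scale variance, from 0 to 0.30.

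**Formulas.**
- Planned: with m and n patients per arm and N = m + n, form all mn between-arm differences. The estimate is their median. The limits are the ordered differences near rank mn/2 ± 1.96·√(mn(N+1)/12).
- Stratified: use only differences within site s, each with weight 1/(Nₛ+1). With T = Σ mₛnₛ/(Nₛ+1) and V = Σ mₛnₛ/(12(Nₛ+1)), the estimate and limits are the differences at cumulative weight T/2 and T/2 ± 1.96·√V.

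**Hand check.** For normal data, removing the between-site variance should multiply the width by about √(1−ICC): √0.90 = 0.949, √0.80 = 0.894, √0.70 = 0.837.

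**Results, no true effect, log-SD 1.0, 5,000 trials per ICC.** The planned width is 3.63–3.64 h throughout. Ratios are stratified/planned, and the SD is the sampling SD of the estimate.

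| ICC | Stratified width (h) | Width ratio | SD ratio | Planned coverage | Stratified coverage |
|---|---|---|---|---|---|
| 0 | 3.67 | 1.010 | 1.006 | 95.4% | 95.4% |
| 0.02 | 3.62 | 0.996 | 1.001 | 95.0% | 94.9% |
| 0.05 | 3.54 | 0.974 | 1.000 | 95.6% | 95.0% |
| 0.10 | 3.41 | 0.941 | 0.985 | 95.6% | 94.9% |
| 0.20 | 3.17 | 0.872 | 0.960 | 96.7% | 94.9% |
| 0.30 | 2.92 | 0.804 | 0.929 | 97.6% | 94.5% |

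Standard errors are at most 0.001 for the width ratio, 0.002–0.003 for the SD ratio and 0.3 points for coverage.

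Each limit moves in by about 3–6 minutes at ICC 0.05–0.10 and 14–22 minutes at 0.20–0.30. The two estimates correlate 0.97–0.99, so most of the narrowing is removed conservatism and little of it is a better estimate.

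**Sensitivity, width ratio at ICC 0.05, 0.10, 0.20, 0.30 (1,000 trials each).**
- Log-SD 0.7: 0.981, 0.952, 0.891, 0.827.
- Log-SD 1.3: 0.969, 0.929, 0.851, 0.771.

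A separately coded simulation with other site sizes, median 48 h and log-SD 0.9 (400 trials each) gave planned/stratified ratios of 1.023, 1.059, 1.137 and 1.244. Inverted, these are 0.978, 0.944, 0.879 and 0.804.

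**The case against.** **The choice is permitted and prespecified.** SAP 3 allows exceptions, item 10 names its method in full, and Protocol 8 attaches adjustment to the logistic and linear models, not to nonparametric methods. This stands: there is no contradiction. But it does not explain why one outcome in 18 lacks the companion result, and a site-stratified rank method is also nonparametric.

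**The size is wholly assumed.** This stands. At ICC 0–0.02 nothing is gained, and at 0.05–0.10 the gain is minutes. The larger gains need ICCs of 0.20–0.30, which the documents neither support nor exclude.

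**Too wide for which target?** The claim holds for the participating hospitals. Against an average over newly drawn hospitals, with a 20% shorter stay, planned coverage was 94.6%, 92.2% and 93.2% at ICC 0.10, 0.20 and 0.30, which is not conservative. The stratified interval did worse: 93.4%, 90.1% and 88.6%. This limits what the stratified interval may be said to describe, and it is a reason to keep the planned one.

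**The remedy assumes one common shift in hours.** Protocol 5.4.2 expects CTCA provision to vary between centres, so that is not assured. With a 20% shorter stay at every site, the mean pooled and stratified shifts were −3.81 and −3.77 h, −3.79 and −3.72 h, −3.81 and −3.67 h, and −3.85 and −3.64 h at ICC 0.05, 0.10, 0.20 and 0.30. The stratified shift is thus about 1–5% smaller on average, and it was up to 12% smaller in one draw of hospitals. Part of what changes is therefore the quantity estimated.

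**Interval and estimate are not all that is reported on stay.** Arm-level descriptive statistics are planned, and continued hospitalisation is costed in the economic analysis. This is fair, but item 10 is still the SAP's only between-arm estimate of stay.

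**Conclusion.** The concern holds as a low-priority improvement. Length of stay is the one outcome with an estimate and 95% CI that has no site-adjusted result. The planned interval is valid. For the participating hospitals it is wider than necessary if stay differs between them.

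Across log-SDs of 0.7–1.3, a stratified interval would be 2–7% narrower at ICC 0.05–0.10 and 11–23% narrower at 0.20–0.30. It would be about 1% wider if hospitals are alike. These figures rest on assumed site sizes, block size, log-normal stay and ICC. No conclusion in the testing hierarchy depends on them.

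**What to change.** Add one sentence to SAP 4.6 item 10: the pooled Hodges-Lehmann/Moses result is the unadjusted analysis, and a site-stratified shift in hours, with a 95% CI from inverting the van Elteren (site-stratified Wilcoxon) test, is reported beside it as the site-adjusted analysis. Always report both, as for the other outcomes, so that no choice is made after seeing the data. State that the stratified interval describes the participating hospitals. If unadjusted-only is deliberate, a sentence in item 10 should say so, although that leaves the width unchanged.

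The cost is that sentence and a short program for weighted quantiles of within-site differences; site is already recorded. The limits are:
- Sites with patients in only one arm contribute nothing.
- GRACE score and previous CAD stay unadjusted, and site enters as strata, not as the SAP's random effect.
- The second-statistician check of results in SAP 5, "Separate programming and checking of primary outcome results and conclusions", would not cover this code, so it needs its own check.
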